3.3.2 Exclusion Criteria

1) Medical History and Concurrent Diseases

- a) Evidence of uncontrolled, active infection, requiring parenteral anti-bacterial, anti-viral or anti-fungal therapy < 7 days prior to administration of study medication
- b) Current or recent (within 3 months of study drug administration) gastrointestinal disease such as chronic or intermittent diarrhea, or uncontrolled disorders that increase the risk of diarrhea, such as inflammatory bowel disease. Non-chronic conditions (eg, infectious diarrhea) that are completely resolved for at least 2 weeks prior to starting study treatment are not exclusionary
- c) Subjects with concomitant second malignancies (except adequately treated nonmelanomatous skin cancers or in situ bladder, breast or cervical cancers) are excluded unless a complete remission was achieved at least 3 years prior to study entry and no additional therapy is required or anticipated to be required during the study period
- d) Subjects with a condition requiring systemic treatment with either corticosteroids (> 10 mg daily prednisone equivalent) or other immunosuppressive medications within 14 days of study treatment. Inhaled or topical steroids, and adrenal replacement steroid doses > 10 mg daily prednisone equivalent are permitted in the absence of active autoimmune disease.
- e) History of medically significant thromboembolic events or bleeding diathesis within the past 6 months, such as cerebrovascular accident (including transient ischemic attacks), pulmonary embolism, pulmonary hemorrhage > 2 teaspoonfuls/24hrs or repeated pulmonary hemorrhage, gastrointestinal hemorrhage requiring transfusion or procedural intervention
- f) Uncontrolled or significant cardiovascular disease including:
 - i) Congestive heart failure New York Heart Association [NYHA] Class 3 or greater within 3 months (Appendix 6)
 - **ii)** History of congenital long QT syndrome or clinically significant ventricular arrhythmias (such as ventricular tachycardia, ventricular fibrillation or Torsade de Pointes). Controlled atrial fibrillation is not an exclusion criterion
 - iii) Active coronary artery disease, unstable or newly diagnosed angina or myocardial infarction in the past 6 months
- g) Inability to tolerate oral medication.
- h) HIV-related disease or known positivity for human immunodeficiency virus (HIV).
- i) History of and chronic hepatitis evidenced by:
 - i) Positive Test for hepatitis B surface antigen
 - ii) Positive test for qualitative hepatitis C viral load (by polymerase chain reaction (PCR)

Note: Participants with positive hepatitis C antibody and negative quantitative hepatitis C by PCR are eligible. History of resolved hepatitis A virus infection is not an exclusion criterion.

- j) Not *applicable; removed per Revised Protocol 02*. NCI CTCAE v4.03 Grade 2 or higher peripheral neuropathy (sensory or motor).
- k) Any other sound medical, psychiatric and/or social reason as determined by the investigator.

- Use of strong inhibitors of CYP3A4 or P-gp within 1 week or 5 half-lives (whichever is longer) or strong inducers of CYP3A4 or P-gp within 2 weeks or 5 half-lives (whichever is longer). See Appendix 3
- m) Current uncontrolled autoimmune pneumonitis
- n) Use of non-oncology vaccines containing live virus for prevention of infectious diseases within 12 weeks prior to study treatment. The use of inactivated seasonal influenza vaccines, eg, Fluzone®, will be permitted on study without restriction.
- o) Uncontrolled endocrine disorder including thyroid disease
- p) Prior organ allograft or allogenic hematopoietic stem cell transplantation (HSCT)
 - i) Participants with active, known or suspected autoimmune disease. Note the following exceptions: Participants with: vitiligo, type I diabetes mellitus, residual hypothyroidism due to autoimmune condition only requiring hormone replacement, euthyroid participants with a history of Grave's disease (participants with suspected autoimmune thyroid disorders must be negative for thyroglobulin and thyroid peroxidase antibodies and thyroid-stimulating immunoglobulin prior to first dose of study treatment), psoriasis not requiring systemic treatment, or conditions expected not to recur in the absence of an external trigger are permitted to enroll.

2) Physical and Laboratory Test Findings

- a) Inadequate bone marrow function defined as:
 - i) Absolute neutrophil count (ANC) < 1,500 cells/mm³ for solid tumors and <1,000 cells/mm³ for hematologic malignancies
 - ii) Platelet count < 100,000 cells/mm³ for solid tumors and <75,000 cells/mm³ for hematologic malignancies
 - iii) Hemoglobin < 8 g/dL
- b) Abnormal blood coagulation parameters:
 - i) PT such that international normalized ratio (INR) is > 1.5x ULN (or > 2.5 x baseline, if a subject is on a stable dose of therapeutic warfarin) or a PTT > 1.2x upper limit of normal (ULN).
- c) Inadequate hepatic function defined as:
 - i) Aspartate aminotransferase (AST) > 3x ULN
 - ii) Alanine aminotransferase (ALT) > 3x ULN
 - iii) Total bilirubin > 1.5 x ULN (except known Gilbert's syndrome, direct bilirubin > 1.5 x ULN);
- d) Inadequate renal function defined as:
 - i) Creatinine clearance (CrCl) \leq 50 mL/minute (either measured or calculated using a standard formula such as Cockcroft and Gault) within 14 days prior to randomization
- e) Any of the following on 12-lead electrocardiogram (ECG) prior to study drug administration, confirmed by repeat.

- i) QRS \geq 120 msec, except right bundle branch block
- ii) QTcF > 450 msec, except right bundle branch block
- f) Inadequate thyroid function

Note: Subclinical hypothyroidism (thyroid-stimulating hormone < 10 mIU/mL) or controlled hypothyroidism on appropriate thyroid supplementation are acceptable if negative for thyroglobulin, thyroid peroxidase antibodies, and thyroid stimulating immunoglobulin.

- g) Weight of < 40 kg.
- 3) Not applicable; removed per Revised Protocol 03. Allergies and Adverse Drug Reaction history of significant allergy or severe drug toxicity to one of the mandatory chemotherapeutic agents or their diluents (e.g. Cremaphor) excludes a subject from that particular arm, except a Grade ≤2 infusion reaction to paclitaxel, with successful subsequent retreatment with premedication.

4) Other Exclusion Criteria

- a) Prisoners or subjects who are involuntarily incarcerated
- b) Subjects who are compulsorily detained for treatment of either a psychiatric or physical (eg, infectious disease) illness
- c) Inability to comply with restrictions and prohibited activities/treatments as listed in Section 3.4
- d) Women who are pregnant
- e) Adolescents who provide active dissent

Eligibility criteria for this study have been carefully considered to ensure the safety of the study subjects and that the results of the study can be used. It is imperative that subjects fully meet all eligibility criteria.

3.3.3 Women of Childbearing Potential

Women of childbearing potential (WOCBP) is defined as any female who has experienced menarche and who has not undergone surgical sterilization (hysterectomy or bilateral oophorectomy) and is not postmenopausal. Menopause is defined as 12 months of amenorrhea in a woman over age 45 in the absence of other biological or physiological causes. In addition, females under the age of 55 years must have a documented serum follicle stimulating hormone, (FSH) level > 40mIU/mL to confirm menopause.

Females treated with hormone replacement therapy, (HRT) are likely to have artificially suppressed FSH levels and may require a washout period in order to obtain a physiologic FSH level. The duration of the washout period is a function of the type of HRT used. The duration of the washout period below are suggested guidelines and the investigators should use their judgement in checking serum FSH levels. If the serum FSH level is >40 mlU/ml at any time during the washout period, the woman can be considered postmenopausal.

- 1 week minimum for vaginal hormonal products, (rings, creams, gels)
- 4 week minimum for transdermal products
- 8 week minimum for oral products

Other parenteral products may require washout periods as long as 6 months.

3.4 Concomitant Treatments

Glucocorticoids may be administered for treatment of infusion reactions and as premedication to prevent infusion reactions.

Palliative radiation therapy to a limited field (eg, painful bone metastasis, painful lumps), if it is not the sole site of measurable and/or assessable disease, is allowed any time during study participation with prior approval of the Sponsor/Medical Monitor.

Subjects with prostate cancer (CRPC and NEPC) are allowed to continue ARD therapy during this trial if the therapeutic agent(s) is (are) not prohibited due to CYP3A4 interactions (eg, enzalutamide is prohibited). Other agents without strong CYP3A4 interactions, such as androgen synthesis inhibitors, gonadotropin realizing hormone analogs, or AR antagonists may be continued if the subject is already on a stable dose.

Subjects are permitted to use topical, ocular, intra-articular, intranasal, and inhalational corticosteroids (with minimal systemic absorption). Adrenal replacement steroid doses > 10 mg daily prednisone are permitted. A brief (<3 weeks) course of corticosteroids for prophylaxis (eg, contrast dye allergy) or for treatment of non-autoimmune conditions (eg, delayed-type hypersensitivity reaction caused by a contrast allergen) is permitted.

Any concomitant therapies within 4 weeks prior to study drug administration and until the final follow-up visit must be recorded on the CRF.

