- d) For Part 1, all subjects must have archival tumor tissue identified and available (if slides are provided, a minimum of 10 (ten) unstained slides with at least 5 micron thick tissue sections are required) **unless a fresh biopsy is provided.** All subjects not providing a fresh biopsy must consent to provide tumor blocks or slides to the sponsor and the availability of the tissue must be confirmed prior to subjects receiving study medication. If an archived tumor specimen is unavailable or unsuitable for this study if it can be performed at minimal acceptable clinical risk as judged by the investigator and if it does not include a target lesion or lesion in an area treated with prior radiation therapy.

For Part 2, both a pre-treatment and on-treatment fresh biopsy must be provided. EOT biopsies must be collected for subjects experiencing PD. For adolescent subjects, fresh biopsies pre- and post-treatment are preferred but not mandated. If a fresh biopsy is not provided, archival tumor tissue is required. The screening tumor tissue for the expansion cohorts enrolled in Part 2 of the study must be shipped as described in the laboratory manual for biomarker testing including identification of select pre-defined genetic biomarkers prior to treatment, with the exception of samples from subjects with NMC, ES, BL, and DHL for which the characterization of fusion proteins is a part of SOC. Subjects whose pre-treatment biopsy yields inadequate tissue quantity or quality will only be eligible if sufficient archival tissue is available, after discussion with the Medical Monitor. If there is only 1 measureable lesion and a core needle biopsy is done (instead of excisional), the lesion may be used as a measureable lesion. If there are more than 1 measureable lesions, the lesion being biopsied should not be a target lesion. Fine needle biopsies are not allowed.

e) Subjects must have a life expectancy of at least 3 months.

- f) Subjects must have an Eastern Cooperative Oncology Group (ECOG) Performance Status of 0 to 1 (Appendix 5).
- g) Subjects who have undergone any major surgery within 4 weeks of study drug administration are excluded. Subjects must have recovered from the effects of major surgery at least 14 days before the first dose of the study drug.
- h) Prophylactic anticoagulation for venous access devices with low-dose heparin or similar (e.g. heparin catheter flush) will be permitted.

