3.6 Treatment Beyond Progression

Evidence supporting the continuation of BMS-986158 monotherapy in subjects with solid or hematologic malignancies beyond progression of their disease is lacking and therefore monotherapy treatment beyond progression will not be allowed. If combination therapy is pursued, subjects receiving BMS-986158 in combination with nivolumab will be permitted to continue on combination therapy beyond initial RECIST v1.1, Lugano 2014 (Appendix 9), or PCWG (Appendix 12) defined PD, as long as they meet the following criteria:

- Investigator-assessed clinical benefit and not having rapid disease progression
- Continue to meet all other study protocol eligibility criteria
- Tolerance of study drug
- Stable performance status
- Treatment beyond progression will not delay an imminent intervention to prevent serious complications of disease progression (eg, CNS metastases)
- Subject provides written informed consent prior to receiving any BMS-986158 plus nivolumab treatment using an ICF describing any reasonably foreseeable risks, discomforts, or other alternative treatment options

The assessment of clinical benefit should take into account whether the subject is clinically deteriorating and unlikely to receive further benefit from continued treatment. All decisions to continue treatment beyond initial progression must be discussed with the BMS Medical Monitor and an assessment of the benefit/risk of continuing with study drug must be documented in the study records. Subjects will be re-consented to explain the rationale for this ongoing treatment.

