8.3.2.1 Efficacy

The first secondary objective (efficacy) will be based on RECIST v1.1 for solid tumors (Appendix 4), Lugano 2014 criteria for hematologic malignancies (Appendix 9), or PCWG3

```
Revised Protocol No.: 07
Date: 18-Mar-2019
```

criteria for prostate cancer (CRPC or NEPC) (Appendix 12) using the following secondary endpoints:

- Best overall response (BOR): defined as the best response designation, recorded between the dates of first dose and the date of first objectively documented progression (per RECIST v1.1 for solid tumors, Lugano 2014 criteria for hematologic malignancies or PCWG3 for prostate cancer) or the date of subsequent therapy, whichever occurs first. CR or PR determinations included in the BOR for solid tumor assessments must be confirmed by a second scan performed no less than 4 weeks, and for hematologic malignancies, no less than 2 weeks after the criteria for response are first met. For subjects without documented progression or subsequent therapy, all available response designations will contribute to the BOR assessment. For subjects who continue treatment beyond progression or begin subsequent therapy, the BOR should be determined based on response designations recorded up to the time of the initial evaluation (RECIST v1.1 for solid tumors, Lugano 2014 criteria for hematologic malignancies or PCWG3 criteria for prostate cancer [CRPC or NEPC]) defined progression or subsequent therapy, whichever occurs first. For those subjects who have surgical resection, only presurgical tumor assessments will be considered in the determination of BOR. A BOR of SD requires a minimum of 49 days on study from date of first dose to the date of the first imaging assessment.
- ORR: defined as the total number of subjects whose BOR is either a CR or PR divided by the total number of subjects in the population of interest

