Investigator reported CR or PR was not always confirmed by a second scan. Therefore, ORR summaries will be presented regardless of confirmation. For subjects without documented progression or subsequent therapy, all available response designations will contribute to the BOR assessment. For subjects who continue treatment beyond progression or begin subsequent therapy, the BOR should be determined based on response designations recorded up to the time of the initial RECIST v1.1 (or by Lugano 2014 criteria for hematologic malignancies, or PCWG3 criteria for prostate cancer [CRPC or NEPC]) defined progression or subsequent therapy, whichever occurs first. For those subjects who have surgical resection, only pre-surgical tumor assessments will be considered in the determination of BOR.

- Duration of Response (DOR): defined as the time between the date of first response (CR or PR) and the date of the first objectively documented disease progression (as determined using RECIST v1.1 for solid tumors, Lugano 2014 criteria for hematologic malignancies, or PCWG3 (including PSA assessments) for prostate cancer [CRPC or NEPC]), or death due to any cause, whichever occurs first. For those subjects who remain alive and have not progressed, duration of response will be censored on the date of last evaluable tumor assessment. Subjects who started subsequent therapy without a prior reported progression will be censored at the last evaluable tumor assessment prior to initiation of the subsequent anticancer therapy. Response duration will only be evaluated in subjects with a BOR of CR or PR. Duration of response will be reported if there are more than 5 CR or PR in a tumor type
- Progression Free Survival (PFS): defined as the time from the first dose of study medication to the date of the first objective documentation of tumor progression or death due to any cause. Clinical deterioration in the absence of radiographic evidence is not considered progression for the purpose of determining PFS. Subjects who neither progressed nor died will be censored on the date of their last evaluable tumor assessment. Subjects who did not have any evaluable on-study tumor assessments will be censored on the date of the first dose of study medication. Subjects who started subsequent therapy without a prior reported progression will be censored at the last evaluable tumor assessment prior to initiation of the subsequent anticancer therapy.

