#### **On-Study:**

- Participants receiving concurrent anti-cancer therapy (defined as chemotherapy, hormonal immunotherapy, non palliative radiation therapy, standard or investigational agents for treatment of NSCLC).
- Participants who received the wrong dose level

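### A target lesion may be irradiated on study, and no rule says whether later scans still count toward best overall response

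*Protocol*

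**What the plan says.** **Radiation.** Protocol 3.4 allows palliative radiation to a limited field, with painful bone metastases and painful lumps as examples, "if it is not the sole site of measurable and/or assessable disease, is allowed any time during study participation with prior approval"; approval rests with the Sponsor/Medical Monitor. Section 3.4.1 bars radiation as concurrent anti-neoplastic therapy. Neither section mentions target lesions. The biopsy rule in 3.3.1 does: "If there are more than 1 measureable lesions, the lesion being biopsied should not be a target lesion".

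**BOR.** In Protocol 8.3.2.1 and SAP 4.2.1 the BOR window ends at first documented progression or at subsequent therapy, whichever is earlier. Without either event, "all available response designations will contribute to the BOR assessment". One local treatment has its own rule: "For those subjects who have surgical resection, only presurgical tumor assessments will be considered in the determination of BOR". The SAP repeats it ("For those subjects who have surgical resection, only pre-surgical tumor assessments will be considered in the determination of BOR"). Appendices 4 (RECIST), 9 (Lugano) and 12 (PCWG3) have no rule for a lesion irradiated on study.

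**Confirmation.** Protocol 8.3.2.1 requires a confirmatory scan. The SAP, which supersedes the protocol's statistical section, does not: "Therefore, ORR summaries will be presented regardless of confirmation".

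**Deviation listing.** SAP 7.2.3 defines on-study concurrent anti-cancer therapy as chemotherapy, "hormonal immunotherapy, non palliative radiation therapy, standard or investigational agents for treatment of NSCLC".

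**The concern.** Radiation can shrink the lesion it is aimed at. If that lesion is in the target sum and later scans still count, the shrinkage is credited to BMS-986158. The authors saw the same problem for resection and wrote a rule for it. They also kept biopsies off target lesions where possible. Palliative radiation has neither protection.

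What is at stake is the tabulated ORR and the boundary count in expansion cohorts of 5 to 9 subjects, where each response carries great weight.

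**Working it through.** **1. Does permitted palliative radiation end the BOR window?**

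- For ending it: the window closes at subsequent therapy, and that term is undefined, so someone could code radiation as such.
- Against ending it: Protocol 3.4 lists palliative radiation as a permitted concomitant treatment, and SAP 7.2.3 confines its radiation deviation to the non-palliative kind. A separate surgery sentence would also be largely redundant if any local treatment already closed the window.

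The second reading is the more natural one, but no sentence settles it. Two programmers could code it differently.

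**2. How much must one irradiated lesion shrink, with the others stable?**

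RECIST and PCWG3 partial response needs a 30% fall in the sum of diameters. If the lesion holds fraction f of the baseline sum, it must shrink by 0.30/f:

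| Equal target lesions | f | Shrinkage needed |
|---|---|---|
| 2 | 1/2 | 60% |
| 3 | 1/3 | 90% |
| 4 | 1/4 | 120%, impossible |

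CT-based Lugano needs a 50% fall in the sum of products (SPD), so 0.50/f: 71% at f = 0.7 and 83% at f = 0.6. A lesion below half the SPD cannot do it alone. The Lugano PET route has no size threshold.

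**3. The plan's own error rates** (SAP Table 5.2-1: 5 then 9 subjects, futility at 0/5, standard-of-care ORR 10%)

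| Final rule | Stated FPR/FNR | Exact, Stage 1 efficacy boundary applied | Exact, no efficacy stop |
|---|---|---|---|
| at least 3/9 (NMC, DHL, TNBC; target 50%) | 10/10% | 9.9/8.0% | 5.1/10.0% |
| at least 2/9 (non-GC-DLBCL, CRPC; target 35%) | 20/20% | 19.4/17.2% | 19.4/17.2% |

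The stated rates reproduce as nominal ceilings. Both documents say there is no stopping for efficacy, so the last column is the base below.

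**4. Effect of one counted response**

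In a 9-subject cohort one response is 1/9 = 11.1 points. Clopper-Pearson 95% intervals are 0.3 to 48.2% for 1/9, 2.8 to 60.0% for 2/9 and 7.5 to 70.1% for 3/9.

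Take one designated non-responder, with true ORR 10% in the other eight. Let r be the responses needed and compare that subject not counted and counted:

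- Stage 1, not counted: Σ(x=1..4) Bin(x; 4, 0.1) × P(Bin(4, 0.1) ≥ r − x). For r = 2: 0.2916 × 0.3439 + 0.0486 + 0.0036 + 0.0001 = 0.153.
- Stage 1, counted: futility is cleared automatically, leaving P(Bin(8, 0.1) ≥ r − 1). For r = 2: 1 − 0.9^8 = 0.570.
- Stage 2, not counted: Σ(x=1..5) Bin(x; 5, 0.1) × P(Bin(3, 0.1) ≥ r − x).
- Stage 2, counted: the same sum with r − 1 − x in place of r − x.

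| Chance of reaching the final boundary | 2/9 rule | 3/9 rule |
|---|---|---|
| Subject in Stage 1: not counted → counted | 15.3% → 57.0% | 3.6% → 18.7% |
| Subject in Stage 2: not counted → counted | 17.0% → 41.0% | 3.8% → 17.0% |

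These are conditional on such a subject existing.

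**5. Unconditional range**

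The documents give no frequency. As an assumption, let each non-responder have chance q of a radiation response, so the apparent rate is 0.10 + 0.90q. The chance of reaching the boundary is then:

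| q | 2/9 rule | 3/9 rule |
|---|---|---|
| 0 | 19.4% | 5.1% |
| 1% | 22.2% | 6.3% |
| 2% | 25.0% | 7.7% |
| 5% | 33.6% | 12.5% |

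**The case against.** **What stands.** The pathway is narrow. It needs a painful lesion in the target sum, other disease, sponsor approval, no progression ("monotherapy treatment beyond progression will not be allowed") and enough shrinkage in that one lesion. Blastic bone lesions are non-measurable, and in prostate cancer bone is read by bone scan outside the target sum. Appendix 12 allows up to 20 target lesions, which dilutes any single one. Prior approval means that the sponsor knows of each case. Central review is possible, and the lesion listings and spider plots would let a reader spot it. ORR is secondary, no hypothesis is tested, and up to 9 subjects may be enrolled per initial cohort whatever the boundary. The figures in step 4 would be the same for any single misclassified response; they measure the small cohorts as much as this gap.

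**What does not.** Approval has no stated target-lesion criterion and is not an analysis rule. The listings and plots do not alter the tabulated ORR or the boundary count.

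**Stronger readings a reader might infer.** One is that the plan discards only post-surgical scans. It does not: BOR also closes at progression and at subsequent therapy. Another is that SAP 7.2.3 proves that radiation leaves the window open. That section lists deviations, and a permitted treatment is not a deviation; its NSCLC wording does not even fit the Initial Expansion tumors. It is supporting evidence only. A third is that ORR in this trial is inflated. Nothing in the documents shows that such a case occurred or how often one would.

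**Conclusion.** The gap is real. A target lesion may be irradiated on study, and neither the BOR definitions nor the response appendices say what happens to later scans. On the more natural reading, post-radiation shrinkage can be counted as an unconfirmed response. This rests on two things: that permitted palliative radiation is not subsequent therapy, which the documents suggest but do not state, and that the irradiated lesion holds enough of the target sum.

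The event is probably uncommon. If it happens once, it adds 11.1 points to a 9-subject ORR, can turn 0/5 into 1/5, and can complete a 2/9 or 3/9 count. Because the two-stage rule guides rather than binds, this is a cheap improvement worth making, not a flaw that undermines the design.

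**What to change.** Extend the surgical sentence in Protocol 8.3.2.1 and SAP 4.2.1, for example: *For a subject whose target lesion is irradiated on study, only tumor assessments made before that radiation count toward CR or PR, under RECIST v1.1, PCWG3 or Lugano 2014.*

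The work is one sentence per document and a programming flag from the on-study RADIOTHERAPY CRF page named in SAP Appendix 1. The documents do not say whether that page records the irradiated site; if not, one field is needed.

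The downside is a small conservative bias. A true response first seen after radiation, including shrinkage in lesions that were not irradiated, is not counted, yet the subject stays in the All Treated denominator. A subject irradiated before the week-8 scan could not be a responder. The sponsor already accepts the same loss for surgery.

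Defining palliative radiation as subsequent therapy would also close the gap, but with the same loss, and if it were treated as anticancer therapy it would censor PFS and duration of response too. Barring radiation to target lesions would protect the endpoint by restricting palliation.
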